12.2.1 Primary efficacy analysis

The primary efficacy variable, change from baseline to Week 6 in the MADRS total score, will be analyzed using a Mixed Model Repeated Measures (MMRM) analysis of all of the post-baseline MADRS total scores through the end of the study (Week 14). The MMRM model will include treatment, visit, treatment by visit interaction, and the baseline MADRS total score as fixed effects, and site as a random effect. Restricted Maximum Likelihood (REML) with an unstructured variance-covariance matrix will be used for estimation in the MMRM analysis. If the model with unstructured covariance does not converge, the model with the non-iterative minimum variance quadratic unbiased estimation will be tried first. If it still fails to converge, the following covariance structures will be tried in order until convergence is reached: toeplitz with heterogeneity, autoregressive with heterogeneity, toeplitz, and autoregressive. Each AZD6765iv dose will be compared with placebo; model-based point estimates for the treatment effects, 95% CIs, and p-values will be calculated.

Subgroup analyses may be performed by age, gender, race, and background antidepressant.

The MMRM analysis of the MADRS total score will be repeated on the PP analysis set to assess the robustness of the results.

For exploratory purposes, the impact of family history of alcoholism and pharmacogenetic biomarkers such as the GABRA2 gene on the primary endpoint and sustained response will be evaluated.

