- Suicidality, as assessed by the C-SSRS
- Change from baseline in cognition as measured by a composite test score comprised of the following CogState test battery tasks: Detection task (DET), Identification task (IDN), One-card Learning task (OCL), and One-back task (OBK)
- Change in severity of dissociative symptoms at each scheduled assessment, as measured by change from baseline in the CADSS total scores
- **Exploratory**
 - Change in anxiety at each scheduled assessment as measured by HAM-A total score
 - Effect of family history of alcohol abuse and GABRA2 on change in MADRS total score and percentage of patients who respond at each scheduled time point
 - Change from baseline in suicidal ideation at each scheduled assessment as measured by change from baseline in S-STS
- **Pharmacokinetics**
 - AZD6765 plasma concentration levels (for population pharmacokinetics [PK] analysis)
- **Pharmacogenetics**
 - Exploratory analysis of the genes involved in the PK, pharmacodynamics (PD), safety, and tolerability related to AZD6765iv treatment may be performed. The polymorphism of genes that may be correlated with the disposition and response to AZD6765iv may be analyzed.
- **Biomarker analysis**
 - Serum samples for optional exploratory biomarker analysis

Statistical methods

Efficacy analyses will be based on the modified intent-to-treat (mITT) analysis set that will include all randomized patients, who received at least 1 dose of IP and who have a baseline MADRS total score assessment and at least 1 post-baseline MADRS total score classified according to their randomized treatment.

Safety and tolerability assessments will be based on the safety analysis set, which will include all randomized patients who are given the IP, and for whom any post-dose data are available, classified according to the treatment actually received.

The primary efficacy variable, change from baseline to Week 6 in the MADRS total score, will be analyzed using a Mixed Model Repeated Measures (MMRM) analysis of all of the post-baseline MADRS total scores through the end of the study (Week 14). The model will include treatment, visit, treatment by visit interaction, and the baseline MADRS total score as fixed effects, and site as a random effect. Restricted Maximum Likelihood (REML) with an unstructured variance-covariance matrix will be used for estimation in the MMRM analysis. Each AZD6765iv dose will be compared with placebo.

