6.3.2.1 Montgomery-Åsberg Depression Rating Scale (MADRS)

The MADRS is a 10-item scale for the evaluation of depressive symptoms ([Montgomery SA, Åsberg M 1979](#)). The MADRS will be administered by a physician, PhD, RN, or other healthcare professional skilled and experienced in the care of this patient population. Each rater administering the MADRS must receive training and certification on the use of the MADRS and must be approved by AstraZeneca or representative.

Each MADRS item is rated on a 0 to 6 scale. Higher MADRS scores indicate higher levels of depressive symptoms. The individual item scores will be recorded on the eCRF. A patient will be classified as in remission if their MADRS total score is ≤ 8 . The MADRS must be administered at designated visits prior to infusion. The MADRS administered at Visits 3, 4, and 5 (prior to infusions 2, 3, and 4) will evaluate depressive symptoms since last infusion; at all other time points MADRS will evaluate depressive symptoms during the past week regardless of the interval between doses/visits.

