12.3 Determination of sample size

The sample size calculation in this study was done to ensure a 90% power to show that at least 1 of the 2 AZD6765 doses will be better than placebo with regard to the primary outcome variable, change in MADRS total score from baseline to Week 6. The sample size was calculated by assuming an anticipated difference of 5.5 units from placebo and a standard deviation of 10 for the change in MADRS total score from baseline to Week 6. Based on the Bonferroni multiplicity adjustment, the one-sided significance level is planned at 1.25%, which yielded a planned sample size of 84 patients per arm required at Week 6 for the primary analysis. Assuming approximately 10% of information will be lost at Week 6 due to dropout, it is estimated that 282 patients (94 patients per arm) will need to be randomized.

The assumptions for the sample size estimation were based on the results of the targeted subgroup (HAM-D-17 ≥ 24 , CGI-S ≥ 5 , QIDS-SR-16 ≥ 19) from previous a Phase II study of D6702C00009. The average treatment difference observed for AZD6765 100 mg and 150 mg versus placebo at Week 3 in this targeted subgroup was about 5.5. With the continuous once-a-week iv treatment, we expect the same treatment effect can be maintained to the primary time point at Week 6. The observed SD in this targeted subgroup was about 10 across the 3 treatment groups from this study. The dropout rates for D6702C00009 study was about 6% at Week 3 and about 19% at Week 8, so we expect about 14% dropout rate by Week 6 and an additional 10% dropout by Week 12. The MMRM approach on the primary variable uses the correlation between visits that allows us to recover some lost information. The correlations among these visits were between 0.4 and 0.7 in Study D6702C00009, so it seems to be reasonable to assume this correlation to be about 0.5. With this assumption, we expect to recover about 30% of the lost information by the MMRM approach (Lu et al 2008).

The sample size for this study was selected to be consistent with the research hypothesis.

The number of patients that will agree to participate in the genetic research is unknown. It is therefore not possible to establish whether sufficient data will be collected to allow a formal statistical evaluation or whether only descriptive statistics will be generated. A SAP will be prepared where appropriate.

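### The primary MADRS model fixes one baseline slope across 11 visits; adding baseline-by-visit is a cheap, low-severity improvement that helps only if the slope changes over time

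*Protocol*

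**What the plan says.** Section 12.2.1 gives the full list of fixed effects: "The MMRM model will include treatment, visit, treatment by visit interaction, and the baseline MADRS total score as fixed effects". Site is random. The synopsis (Statistical methods) repeats the list. No baseline-by-visit term appears in either place. The analysis uses every post-baseline MADRS total score to Week 14, and "Restricted Maximum Likelihood (REML) with an unstructured variance-covariance matrix will be used for estimation".

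The MADRS row of Table 4 gives 11 post-baseline assessments: Visits 3, 4, 5, 8, 11, 12, 13 (Week 6), 14, 15, 16 (Week 12) and the Week 14 follow-up.

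Section 6.3.2.1 sets the recall period: "The MADRS administered at Visits 3, 4, and 5 (prior to infusions 2, 3, and 4) will evaluate depressive symptoms since last infusion". Elsewhere in the schedule the scale covers the past week.

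**The concern.** The model lets the mean, the treatment effect, the variance and every covariance differ by visit, yet holds the effect of baseline constant. A score taken a few days after baseline, over a shorter recall period, need not relate to baseline as a score six or twelve weeks later does. If it does not, the early visits help to set a slope that is then applied at Week 6 and Week 12, where it fits less well. Chance baseline imbalance would be adjusted with a suboptimal slope, and the residual variance at those visits would be larger than necessary.

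The model supplies both the primary Week 6 tests and the key secondary Week 12 tests. Administrative Change 1 already shows concern about power: it revises the expected effect from 5.5 to 4.5 points and puts the power of the first test at about 82%.

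**Working it through.** **1. The plan's own figures.** Section 12.3 uses a difference of 5.5, SD 10, one-sided alpha 0.0125 and 90% power.
- Normal approximation: n = 2 × (10/5.5)² × (2.2414 + 1.2816)² = 82.1, so 83 per arm. The noncentral t gives 84 (power 90.25%), as stated.
- 84/0.90 gives 94 per arm, 282 in total.
- 14% dropout × (1 − 0.30 recovered) = 9.8%, matching the 10% information loss.
- At 4.5 points and 84 per arm, the standard error is 10 × √(2/84) = 1.543 and 4.5/1.543 = 2.916. Normal power is 75.0% at one-sided 0.0125 and 83.1% at one-sided 0.025 (noncentral t: 74.3% and 82.6%). Administrative Change 1 gives about 74% and 82%.

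These all reproduce.

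**2. Large-sample cost of a common slope.** The relative excess variance at Week 6 is

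(Week 6 slope − common slope)² × Var(baseline) / residual variance at Week 6.

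Assumptions that are not in the documents: baseline MADRS SD 4 to 6; slope of change on baseline either constant at −0.3 or drifting from about −0.05 or −0.1 at the first visits to −0.5 or −0.55 at the last; residual SD either constant at 10 or rising from 6 to 10.5. The two drift patterns have Week 6 slopes of about −0.34 (milder) and −0.50 (stronger), and the Week 6 residual variance is about 100. The common slope is the generalised least squares value for each correlation structure.

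| Assumed case | Common slope | Excess variance at Week 6 | Power, common slope |
|---|---|---|---|
| Equal slopes | −0.300 | 0 | 83.1% |
| Milder drift, constant SD, baseline SD 5 | −0.300 | 0.04² × 25/100 = 0.04% | 83.0% |
| Stronger drift, constant SD, baseline SD 6, AR 0.7 | −0.318 | 0.182² × 36/100 = 1.2% | 82.6% |
| Milder drift, rising SD, baseline SD 5, AR 0.4 | −0.190 | 0.15² × 25/100 = 0.56% | 82.9% |
| Stronger drift, rising SD, baseline SD 6, compound symmetry 0.5 | 0.008 | 0.508² × 36/100 = 9.3% | 79.7% |

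The last row is extreme. Its common slope lies outside the range of the assumed visit slopes, because generalised least squares can give later, more variable visits negative weight. Its penalty equals 0.093 × 252, or about 23 patients.

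**3. Cost of the interaction.** It adds 10 fixed-effect parameters and leaves the 66 covariance parameters unchanged. The variance cost at Week 6 is at most about 1/(252 − 4) = 0.4%, which takes power from 83.1% to 82.9%. Set against the table, adding the term changes power by between about −0.1 (milder drift, constant SD) and +3.2 points, or by about −0.2 if the slopes are equal.

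**4. Simulation of both models.** 94 per arm, effect 4.5, unstructured covariance, no site effect, 1,200 runs per scenario.

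| Scenario | Variance ratio, common / interaction | Power, common | Power, interaction |
|---|---|---|---|
| Equal slopes (three dropout settings) | 0.99 to 1.00 | 84.8 to 85.9% | 84.8 to 85.8% |
| Drift, no dropout | 1.024 | 87.7% | 88.3% |
| Drift, about 12% outcome-dependent MAR dropout | 1.029 | 82.8% | 83.9% |
| Drift, about 13% dropout related to baseline in opposite directions by arm | 1.023 | 87.2% | 84.5% |

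Neither model was biased in the first three rows. In the last, the common-slope estimate was biased by −0.27 points (about 6% of 4.5) and the interaction model by −0.04 (Monte Carlo standard error about 0.045). The higher common-slope power there reflects that bias, which exaggerated the effect; it is not a gain in precision.

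**The case against.** The strongest defence is that nothing here is an error. Under randomization the Week 6 contrast from the planned model is unbiased without dropout, and in the simulation it was also unbiased under outcome-dependent MAR dropout. A reader might infer that the single slope invalidates or generally biases the primary comparison. The documents do not support that: bias needed drifting slopes together with baseline-related dropout running in opposite directions by arm, and nothing in the protocol points to such dropout.

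A reader might also infer that the protocol shows the slopes to be unequal, or that the interaction is always better and free. Neither holds. The recall-window text covers 3 of the 11 visits and makes unequal slopes plausible without establishing them; 7 of the 11 fall between Week 4 and Week 14. If the slopes are equal there is no gain and a small loss.

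Nor does the argument carry over to the other scales analysed with the same model. The recall text concerns MADRS only. In Table 4, HAM-A, SDS and QIDS-SR-16 have no assessment at Visits 3 to 5, and CGI-S has only Visit 5.

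Finally, Section 12.2 leaves detail to a SAP that is to be final before unblinding. This is only a partial answer, because the protocol lists the fixed effects explicitly. It does mean that the refinement can still be made cleanly.

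**Conclusion.** A low-severity, optional improvement to a valid model. The single baseline slope is a stated choice, and the case for relaxing it is an asymmetry: a loss of at most about 0.4% of variance (about 0.2 power points) if slopes are equal, against a typical gain of about 0 to 3% (around 1 power point or less) if they drift. The gain reaches about 9% (about 3 power points) only with the strongest assumed drift, the largest assumed baseline SD and residual SD that rises over visits. The term also protects against a bias of about 0.3 points in one specific dropout pattern. All of these sizes rest on assumed baseline SDs, slopes and residual SDs; the documents supply none of the visit-level values needed to narrow them.

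**What to change.** Add baseline MADRS-by-visit as a fixed effect in the primary MADRS model, in the synopsis and Section 12.2.1 and correspondingly in the SAP, before unblinding. The same fitted model then serves Week 6 and Week 12. The change is one term in the model statement and needs no new data. Adding a matching term to the models for the other scales is optional and would need its own justification.

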12.2.2 Secondary efficacy analyses

Change from baseline in the MADRS total score at Week 12 and at the other scheduled visits will be assessed using the MMRM analysis used for the primary efficacy variable. At each visit, each AZD6765iv dose will be compared with placebo and model-based point estimates for the treatment effects, 95% CIs, and p-values will be calculated. The MMRM analysis of

the MADRS total score will be repeated on the PP analysis set to assess the robustness of the results.

For the other continuous secondary efficacy variables (change from baseline in the CGI-S score, the SDS total score, the HAM-A total score, and the QIDS-SR-16 total score at each scheduled assessment), the same MMRM approach as for the primary efficacy variable will be used for the analysis.

For the binary secondary efficacy variable with only a single post-baseline assessment (sustained response), the analysis will be performed using logistic regression with independent variables of treatment and the baseline MADRS total score.

For the binary secondary efficacy variables with multiple post-baseline assessments (response, remission, and CGI-I response), the analysis will be performed using a generalized linear model of the repeated measures. A logit link function will be used and the statistical inferences will be based on Generalized Estimating Equations (GEE). Independent variables will be treatment and a baseline measurement related to the dependent analysis variable. For response and remission, the baseline MADRS total score will be used as the baseline measurement; for CGI-I response, the baseline CGI-S score will be used.

[figure not shown]
The exploratory variables of continuous and binary types will be evaluated the same way as for the secondary efficacy variables

Descriptive statistics will be used to summarize all efficacy endpoints, including individual item scores.

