The comparator in this study is placebo (0.9% saline), which will also be administered intravenously. The infusion will be a final volume of 100 mL given at an infusion rate of 1.67 mL/min over 60 minutes. Patients assigned to the placebo treatment group will receive multiple infusions of placebo during the treatment period according to the same schedule as the patients assigned to the AZ6765iv dose groups.

Duration of treatment

Eligible patients will have a screening period of up to 6 weeks. Following the screening period, patients will enter a 12-week double-blind treatment period and a 14-day follow-up period.

Outcome variables:

- **Efficacy**

Primary outcome variable:

- Change from baseline to Week 6 in the MADRS total score

Secondary outcome variables:

- Change from baseline to Week 12 in the MADRS total score
 - Percentage of patients with sustained response, defined as a $\geq 50\%$ reduction from baseline in the MADRS total score at Week 6 and which is maintained through Week 12
 - Change from baseline in the MADRS total score at each scheduled assessment
 - Percentage of responders at each scheduled assessment where responders are defined as patients with a $\geq 50\%$ reduction from baseline in MADRS total score
 - Percentage of patients who are remitted at each scheduled assessment where remission is defined as MADRS total score ≤ 8
 - Change from baseline in functional impairment at each scheduled assessment, as measured by the change from baseline in the SDS total score
 - Change in severity of depressive symptoms at each scheduled assessment as measured by change from baseline in the CGI-S score
 - Change in severity of depressive symptoms at each scheduled assessment as measured by the CGI-I response. Response in CGI-I is based on whether or not the CGI-I score is ≤ 2 (very much improved or much improved).
 - Change from baseline in self-rated severity of depressive symptoms at each scheduled assessment as measured by QIDS-SR-16 total score
- **Safety**
 - Adverse events (AEs)/serious adverse events (SAEs), including their severity
 - AEs leading to treatment discontinuation or study withdrawal

- Suicidality as measured by AEs of suicidality, suicidal ideation, suicide attempts, and suicide completion
- Other significant AEs (OAEs), other AEs of special interest
- Change from baseline in physical examination results, weight, body mass index (BMI), vital signs, clinical laboratory test results, and ECG results

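### The GEE for response, remission and CGI-I response lists no visit or treatment-by-visit term, so it gives one pooled odds ratio per dose although the endpoints are defined visit by visit

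*Protocol*

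**What the plan says.** The secondary outcome variables in the protocol synopsis are visit-specific:

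- Response: "Percentage of responders at each scheduled assessment where responders are defined as patients with a" reduction of at least half from baseline in MADRS total score.
- Remission: "Percentage of patients who are remitted at each scheduled assessment where remission is defined as MADRS total score" of 8 or less.
- CGI-I: "Change in severity of depressive symptoms at each scheduled assessment as measured by the CGI-I response".

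Section 12.2.2 sets the analysis: "For the binary secondary efficacy variables with multiple post-baseline assessments (response, remission, and CGI-I response") a generalized linear model of the repeated measures is fitted with a logit link and GEE inference. The covariates follow: "Independent variables will be treatment and a baseline measurement related to the dependent analysis variable". The baseline measurement is the MADRS total score for response and remission, and the CGI-S score for CGI-I response. The statistical methods part of the synopsis gives the same list. Exploratory binary variables are to be handled in the same way.

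The continuous endpoints are treated differently. Section 12.2.1 says "The MMRM model will include treatment, visit, treatment by visit interaction, and the baseline MADRS total score as fixed effects". For MADRS change, Section 12.2.2 adds: "At each visit, each AZD6765iv dose will be compared with placebo and model-based point estimates for the treatment effects". No such sentence follows for the binary variables.

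**The concern.** The stated model and the stated endpoint do not match. A mean model with only treatment and baseline assumes the same response probability at every visit for a given arm and baseline score, and hence a single odds ratio per dose. It has no parameter from which a Week 6 or Week 12 contrast could be read.

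The pooled value is also hard to interpret, because it averages unlike visits. For response and remission these run from the second infusion to a follow-up visit about 14 days after the last dose. They include three early ratings (Visits 3, 4 and 5) with a different recall period: the MADRS there "will evaluate depressive symptoms since last infusion; at all other time points MADRS will evaluate depressive symptoms during the past week". If the treatment effect changes over time, the pooled odds ratio depends on how many visits the calendar places in each phase.

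At stake is the modelled dose-versus-placebo comparison of three secondary endpoints, with interval and p-value, at the times the trial is built around.

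**Working it through.** No figure in the protocol depends on this model, so there is none to reproduce. The check has four steps.

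**1. Terms side by side.**

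| | Continuous endpoints (12.2.1, 12.2.2) | Response, remission, CGI-I response (12.2.2 and synopsis) |
|---|---|---|
| Treatment | yes | yes |
| Baseline | yes | yes |
| Visit | yes | not listed |
| Treatment by visit | yes | not listed |
| Each dose vs placebo at each visit | stated for MADRS change | not stated |

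**2. What the listed model can return.** For patient i at visit v:

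logit P(response) = b0 + b1·[50 mg] + b2·[100 mg] + b3·baseline

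The right-hand side does not contain v. The odds ratio against placebo is exp(b1) or exp(b2) at every visit. The working correlation affects weighting and precision; it does not create visit-specific means.

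**3. Visits and parameters (Table 4).** Post-baseline MADRS: Visits 3, 4, 5, 8, 11, 12, 13, 14, 15, 16 and Week 14, so 11. CGI-I: the same without Visits 3 and 4, so 9.

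- Listed model: 1 + 2 + 1 = 4 mean parameters.
- With visit and treatment-by-visit, 11 visits: 1 + 2 + 10 + 20 + 1 = 34.
- With both terms, 9 visits: 1 + 2 + 8 + 16 + 1 = 28.

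**4. Size, under assumed rates.** The protocol gives no response rates, so both sets below are assumptions. With complete data and an exchangeable working correlation, a model whose covariates do not vary within a patient weights every visit equally. The pooled odds ratio is then that of the visit-averaged percentages. (Baseline is left out of the hand calculation.)

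*Set A: effect peaks at Week 6, then fades.*

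| Visit | 3 | 4 | 5 | 8 | 11 | 12 | 13 (W6) | 14 | 15 | 16 (W12) | W14 |
|---|---|---|---|---|---|---|---|---|---|---|---|
| Placebo % | 2 | 4 | 7 | 13 | 18 | 22 | 26 | 28 | 29 | 30 | 30 |
| Active % | 3 | 7 | 13 | 25 | 33 | 40 | 46 | 44 | 40 | 36 | 32 |
| Odds ratio | 1.52 | 1.81 | 1.99 | 2.23 | 2.24 | 2.36 | 2.42 | 2.02 | 1.63 | 1.31 | 1.10 |

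Means: placebo 209/11 = 19.0%, active 319/11 = 29.0%. Pooled odds ratio = (0.29/0.71)/(0.19/0.81) = 1.74. A simulated GEE with the listed terms (2,000 per arm, one active arm) fitted 19.5% and 29.0% at every visit, odds ratio 1.68. Adding visit and treatment-by-visit gave 2.31 at Week 6 and 1.29 at Week 12. The pooled figure is therefore too low for Week 6 and too high for Week 12.

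*Set B: both arms 3% at Visit 3, rising to 25% (placebo) and 40% (active) at Week 6, then flat.* Week 6 odds ratio = (0.40/0.60)/(0.25/0.75) = 2.0. Take visit days of about 3, 5, 8, 15, 26, 33, 40, 54, 68, 82 and 96, with a linear rise from day 3 to day 40. The fractions of the full rise are then 0, 0.054, 0.135, 0.324, 0.622, 0.811 and five times 1, mean 6.946/11 = 0.631. Averages: placebo 3 + 22 × 0.631 = 16.9%; active 3 + 37 × 0.631 = 26.4%. Pooled odds ratio = (0.264/0.736)/(0.169/0.831) = 1.76. Other curve shapes gave values down to 1.64. Simulation at trial size (94 per arm, 11 visits) gave a median of 1.67 against 1.97 at Week 6.

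**The case against.** The best defence has four parts.

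- **The SAP may add the terms.** Section 12.2 defers details to a SAP, and the GEE sentence is brief; it does not name a working correlation either. But the covariate list is not left open. It is stated flatly in two places, while the MMRM text spells out its visit terms. A SAP that follows the list keeps the mismatch, and one that adds the terms departs from the protocol.
- **Percentages by visit will still be shown.** This stands. Sections 12.2 and 12.2.2 provide for descriptive frequencies of all efficacy endpoints. A reader might infer that the endpoints cannot be reported by visit at all, and that goes too far. What is lost is the modelled comparison.
- **A visit-averaged effect is a legitimate target.** It is, but it is not the one the outcome list defines.
- **Little hangs on it.** Largely true. These are non-key secondary and exploratory variables without multiplicity adjustment.

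Two stronger readings are tempting, and the protocol does not support them.

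- A reader might say that the early visits only dilute the estimate because nobody can have responded yet. Section 1.4 reports superiority over placebo 72 hours after a single 100 mg infusion, including on a 50% MADRS reduction. The recall change also concerns the MADRS only, and CGI-I does not start until Visit 5.
- A reader might also infer bias from unequal dropout, since the visit mix would then differ by arm. Under no effect and an assumed 30% versus 18% dropout, the log odds ratio moved by only about 0.05, against a standard error of about 0.23. The protocol projects only overall dropout (14% by Week 6 and a further 10% by Week 12). Sections 5.9 and 12.2.6 bring discontinued patients back for these ratings and use the retrieved data.

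**Conclusion.** The point holds as a mismatch between the listed GEE model and its endpoints. As written, the model gives one odds ratio per dose for each of response, remission and CGI-I response, and no modelled contrast at Week 6, Week 12 or any other visit. That conclusion follows from the listed terms and needs no assumption.

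The size does rest on assumptions. With an assumed Week 6 odds ratio of about 2.0, the model would report about 1.7 (1.64 to 1.76 across the curve shapes tried). If the effect fades after Week 6, as in Set A, the same figure overstates Week 12.

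The primary endpoint and Week 12 MADRS change use the MMRM, and sustained response uses a logistic regression on a single outcome, so none of the three is touched. The change should be made, but the trial's main conclusion does not depend on it.

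**What to change.** In Section 12.2.2 and in the statistical methods part of the synopsis, list the GEE independent variables as treatment, visit (categorical), treatment by visit, and the relevant baseline measurement, as in the MMRM. Add that each dose is compared with placebo at each scheduled assessment, with odds ratio, 95% confidence interval and p-value.

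Before unblinding, fix a fallback for early visits with too few events for the model to converge. Remission is the likeliest case, since 34 mean parameters may not all be estimable.

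The cost is about one sentence in each place and a small programming change; no new data are needed. The price is wider intervals for visit-specific odds ratios than for a pooled one. If a visit-averaged effect is also wanted, it can be reported as an additional, labelled summary from the same model.
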